Other Agent: Temozolomide, commercially available

SCHEMA

Cycle 1 and subsequent cycles.

Methoxyamine (MX) will be given as a single one hour infusion every 28 days.

Temozolomide (TMZ) will be given orally for 5 days every 28 days on days 1-5. It will be administered within five minutes of initiation of methoxyamine

Cycles are concluded every 28 days.

Week1	Day1	2	3	4	5
MX	↔				
TMZ	↓	↓	↓	↓	↓

Note:

Treatment toxicities for cycle 1 will be considered for dose limiting toxicity (DLT) attribution. Dose modifications are allowed for cycle 2 and beyond.

Cohort A (eligible patients with no CNS disease)

DOSE-ESCALATION SCHEDULE		
Dose Level	Dose	
	TMZ (mg/m ² /day) x 5days	MX (mg/m ²)
Level -1	100	15
Level 1	150	15
Level 2	150	30
Level 3	150	60
Level 4	150	90
Level 5	150	120
Level 6	150	150
Level 7	200	150

Cohort B (eligible patients with CNS disease)

DOSE-ESCALATION SCHEDULE		
Dose Level	Dose	
	TMZ (mg/m ² /day) x5days	MX (mg/m ²)
Level -1	75	15
Level 1	100	15
Level 2	150	15

Level 3	150	30
Level 4	150	60
Level 5	150	120
Level 6	150	150
Level 7	200	150

For each cohort, 3 patients will be entered sequentially to each dose level.

- If none of the 3 patients at a dose level experience dose limiting toxicity (DLT) during the first cycle, new patients may be entered at the next dose level.
- If 1/3 patients experiences DLT during the first cycle, up to 3 more patients will be treated at the same dose level. If the 1st patient in the expanded cohort (4th at the given DL), experiences no DLT, then the remaining 2 patients can start treatment without a necessary delay.
 - As of protocol v22, if 1/3 patients experience any DLT that is not of a CNS nature in Cohort B dose level 6, we will continue dose escalation to dose level 7 since we have already treated three subjects in Cohort A dose level 6 and seven subjects in Cohort A dose level 7, none of whom experienced non-CNS toxicities
- If 2 or more experience DLT during the first cycle, no further patients are started at that dose and the MTD is the highest dose level in which <2 (of 6) patients develop DLT.
- If the final dose level is deemed the MTD, 6 patients will be treated at this dose level, even if a DLT has not been observed.

Select non-hematologic grade 3 or 4 or hematologic grade 4 drug-related toxicities (CTC version 3.0) occurring in the first 28 days of study will be considered a DLT.

TABLE OF CONTENTS

	Page
SCHEMA	4
1. OBJECTIVES	7
2. BACKGROUND	7
3. PATIENT SELECTION	11

1. OBJECTIVES

- 1.1 To determine the maximum tolerated dose of methoxyamine given in conjunction with temozolomide in patients with and without CNS disease.
- 1.2 To determine the dose limiting toxicities of the combination of methoxyamine and temozolomide in patients with and without CNS disease.
- 1.3 To determine the pharmacokinetics of these two agents when given alone or in combination, as well as the pharmacokinetic profile of methoxyamine after a single one-hour IV administration.
- 1.4 To determine relative DNA damage, as single or double strand breaks by comet assay in blood mononuclear cells which will serve as a surrogate for tumor response to the drug combination.

2. BACKGROUND

Base excision repair (BER) is a fundamental cellular process that reduces the cytotoxicity of alkylating agent chemotherapy. Heretofore, no therapeutic agents have targeted this DNA repair pathway.

Methoxyamine (MX, NSC-3801) is a small organic amine that inhibits base excision repair (BER) by covalently binding to apurinic/apyrimidinic (AP) sites in DNA (1). It has been demonstrated that MX alters the AP site structure by forming a covalent linkage with the aldehyde moiety to form an MX-bound AP site that is refractory to the catalytic activity of the apurinic/apyrimidinic endonuclease (APE), leading to the interruption of BER. Therefore, MX has been studied as a structural modulator of AP sites to enhance therapeutic effect of alkylating agents such as temozolomide (TMZ, NSC-362856).

TMZ is a therapeutic alkylating agent that is efficacious in the treatment of gliomas, melanomas, carcinoid tumors and Hodgkin's lymphoma. However, drug resistance remains a critical problem, often resulting in treatment failure in clinical use. A major obstacle to effective treatment with TMZ in cancer is the presence of elaborate mechanisms of DNA repair. For instance, TMZ forms O⁶-methylguanine (O⁶mG), 7-methylguanine (N7mG), and 3-methyladenine (N3mA) DNA adducts that are repaired by at least two mechanisms. The O⁶mG DNA adduct, a cytotoxic and genotoxic lesion, is repaired by O⁶-methylguanine DNA-methyltransferase (MGMT). MGMT activity is a major mechanism of resistance to alkylating agents. In contrast, cell death caused by O⁶mG adducts is promoted by the mismatch repair (MMR) system, such that, deficiency in MMR is associated with pronounced resistance to alkylating agents. N7mG and N3mA DNA adducts are removed by the base excision repair (BER) pathway. BER, is an important drug resistant factor because it recognizes a variety of substrates and has the ability to rapidly and efficiently repair these DNA lesions. BER is the major pathway that protects cells against the potentially harmful effects of spontaneously and chemically occurring DNA damage, including (i) inappropriate bases; (ii) abasic sites that are

formed by enzyme-catalyzed, spontaneous or chemical-induced base release; and (iii) DNA single strand breaks produced during the processing of damaged DNA. Efficient BER minimizes the impact of these lesions in normal and tumor cells. Thus, when BER is disrupted, these abundant N-methylated DNA adducts and intermediates generated in the repair process become highly cytotoxic. Most importantly, BER disruption is able to bypass other resistance factors such as MMR defects and high MGMT activity.

In several preclinical studies, we have demonstrated improved therapeutic efficacy of alkylating agents by blocking BER with MX (2,3). We have demonstrated in *in vivo* studies that MX potentiates the antitumor effect of TMZ in human tumor xenografts in nude mice. Mice carrying SW480 colon cancer tumors (AGT expressing, MMR wt and p53 mutant) treated with MX (2 mg/kg) plus TMZ (120 mg/kg) had cessation of tumor growth lasting 50±13 days and very slow regrowth, yielding tumor growth delays of 70±14 days ($p < 0.002$) compared with untreated tumors. In contrast, TMZ (120 mg/kg) combined with O6benzylguanine (BG, a new therapeutic agent being tested in clinical trials), gave rise to a tumor growth delay (T2x-C2x) of 25±2.4 days but was accompanied by significant weight loss (maximum body weight loss from 26 to 20 g, 23%) and very low leukocyte counts (90% decreased) 5 days after the last treatment. Thus, compared to BG+TMZ, treatment with MX+TMZ was associated with less body weight loss and less myelosuppression (3). Therefore, MX inhibition of DNA BER is a promising strategy to sensitize tumor cells to therapeutic alkylating agents.

In this first in human phase I clinical trial, methoxyamine was administered as a 5-day continuous intravenous infusion based on animal data. Dosing started at a MX dose of 15 mg/m²/day for 5 days and plasma samples were collected and analyzed for MX using validated methods. Pharmacokinetic parameters were derived using a single compartment iv infusion model and plasma methoxyamine concentrations from 5 patients across 15 dosing cycles using WINNONLIN PK model 2 software.

[figure not shown]

$$A_{inf} = A(1-e^{-kt}) = 59.50 \text{ mg} (1-e^{-(0.0153/\text{h})(1 \text{ h})}) = 0.90 \text{ mg}$$

$$(k = 0.693/T_{1/2} = 0.693/45.26 \text{ h} = 0.0153/\text{h})$$

Therefore, the total methoxyamine dose (A_{total}) given over 60 minutes by intravenous infusion needed to maintain a C_{max} of 41.4 ng/mL over 60 minutes was estimated as:

$$A_{total} = A + A_{inf} = 59.50 \text{ mg} + 0.90 \text{ mg} = 60.40 \text{ mg}$$

The estimated total dose of methoxyamine given over a 60 minute i.v. infusion needed to produce a Cmax of 41.40 ng/mL (60.40 mg) corresponds to 30 mg/m² (assuming an average BSA of 2 m²). Decreasing this calculated dose by 50% to 15mg/m² provides a rational and safe starting methoxyamine dose to administer intravenously over 60 minutes.

In sum, a single dose of MX administered by 60 minute iv infusion in patients enrolled at dose level 1 (15 mg/m²), represents a conservative initial dose level based on human PK parameters obtained from five patients who received methoxyamine at doses of 15 mg/m²/day IV over five days for a total of fifteen cycles.⁴ This dose was calculated so that expected peak concentration following a single 60 minute IV infusion at dose level 1 will be approximately half the observed maximum concentration observed following 5 day intravenous MX infusion.

Temozolomide is now standard treatment for patients with high-grade gliomas⁵ and is often used in patients with metastatic brain tumors as a radiosensitizer or as a single agent therapy. Temozolomide has excellent brain penetration. However, more than half of all GBM patients have MGMT-induced resistance to this agent.⁶ The FDA noted that there was neurotoxicity as DLT from combining temozolomide with methoxyamine in animal toxicology studies and they advised us to exclude patients with brain metastasis or glioma from the initial Phase I study. We now propose to expand the scope of this study while maintaining the original aims by adding a “dose behind” cohort of patients with brain metastasis or glioma. This cohort will be treated with a 1 hr infusion MX dose that is one dose level below that of patients currently enrolling with advanced malignancies but

without brain disease. Patients will receive the dose-level appropriate temozolomide dose. However, since many of these patients will have received prior temozolomide, the initial dose level -1 will be 100 mg/m² of TMZ orally on days 1-5 of a 28-day cycle and 15 mg/m² of MX i.v. over one hour on day 1. Once patients without brain disease have accrued to dose level 2 of MX, we will begin to enroll patients with brain metastasis or gliomas at dose level 1.

3. PATIENT SELECTION

Given the animal toxicity data and CNS involvement of a proportion of eligible patients, two cohorts of eligible patients will be enrolled in the trial:

- Cohort A will include patients **with no** CNS disease
- Cohort B will include patients **with** CNS disease (including recurrent or progressive malignant gliomas and/or brain metastatic disease). Brain metastases do not have to be new to participate in this study.

Inclusion of two separate cohorts was chosen, because this design will allow us to address toxicity concerns generated by the animal studies in a cohort of patients with no CNS disease (cohort A) where development of potential treatment-related CNS toxicity will not be confounded by pre-existing or disease-progression-related symptoms. Inclusion of patients with CNS disease in cohort B will allow us to evaluate the combination in the group of patients where TMZ is currently extensively evaluated and used.

3.1 Eligibility Criteria

- 3.1.1 Patients must have a histologically confirmed solid tumor that is considered incurable and is not amenable to conventional surgical, radiation therapy or chemotherapy treatment programs.
- 3.1.2 Prior chemotherapy and/or radiation are allowed. At least 3 weeks must have elapsed since prior large-field radiation therapy; patients must have been off previous anti-cancer therapy for at least 3 weeks (6 weeks for mitomycin-C and nitrosoureas); and recovered from all treatment related toxicity to \leq grade 1 according to NCI CTCAE version 3.0 (with the exception of alopecia and radiation-induced taste changes). Prior temozolomide treatment is not restricted.
- 3.1.3 Age \geq 18 years.
- 3.1.4 ECOG performance status \leq 2 (Karnofsky \geq 50%, see Appendix A).
- 3.1.5 Life expectancy \geq 12 weeks.

3.1.6 Patients must have normal organ and marrow function as defined below:

- absolute neutrophil count	$\geq 1,500/\mu\text{l}$
- platelets	$\geq 100,000/\mu\text{l}$
- hemoglobin	$\geq 10.0 \text{ g/dl}$
- total bilirubin	$\leq 1.5 \text{ mg/dl}$
- AST(SGOT) normal	$\leq 2.5 \times \text{institutional upper limit of}$
- creatinine	$\leq 1.5 \text{ mg/dl}$
	and/or
- creatinine clearance	$\geq 60 \text{ mL/min}/1.73 \text{ m}^2$

3.1.7 Patients with known primary or metastatic CNS disease, are eligible for participation in cohort B, but not in cohort A.

3.1.8 Women of child-bearing potential and men must agree to use adequate contraception (hormonal or barrier method of birth control; abstinence) prior to study entry and for the duration of study participation. Should a woman become pregnant or suspect she is pregnant while participating in this study, she should inform her treating physician immediately.

3.1.9 Ability to understand and the willingness to sign a written informed consent document.

3.2 Exclusion Criteria

3.2.1 Patients may not be receiving any other investigational agents or have received other investigational agents for at least 3 weeks.

3.2.2 Uncontrolled intercurrent illness including, but not limited to, ongoing or active infection, symptomatic congestive heart failure, unstable angina pectoris, cardiac arrhythmia, or psychiatric illness/social situations that would limit compliance with study requirements.

3.2.3 Pregnant and lactating women are excluded from this study because the methoxyamine and temozolomide combination is likely to be teratogenic.

3.2.5 NYHA classification III or IV heart disease

3.2.6 Patients with known primary or metastatic CNS disease (cohort B) are not eligible if they have a mini mental status exam score < 15 (per Appendix D) or evidence of leptomeningeal disease.

3.2.7 Patients with pre-existing neurologic toxicity $>$ grade 1 (as per

CTCAE, version 3.0) are not eligible for participation in cohort A. Patients screened for participation in cohort B with pre-existing neurologic toxicity > grade 2 (as per CTCAE, version 3.0) are not eligible, unless pre-existing neurotoxicity is documented in detail and patient's participation in the trial has been approved by the neuro-oncology team at participating institutions.

3.3 Inclusion of Women and Minorities

Both men and women of all ethnic groups are eligible for this trial.

4. TREATMENT PLAN

To enter eligible patients on study, investigators will register patients by contacting the study coordinator for this trial. The following information will be requested: a registration card, copy of the informed consent, and copy of the signed eligibility criteria from the study protocol. These must be submitted prior to a patient starting treatment and placed in the chart.

4.1 Agent Administration

For all cycles, TMZ will be given orally for 5 days every 28 days. MX will be given as a single one-hour IV infusion every 28 days. Temozolomide will be administered within 5 minutes following the initiation of methoxamine.

Patients will be treated and monitored in the inpatient setting (Clinical Research Unit) during MX administration (on cycle 1 day 1). A physician will be onsite within the hospital in case an adverse event occurs.

Cohort A (eligible patients with no CNS disease)

DOSE-ESCALATION SCHEDULE		
Dose Level	Dose	
	TMZ (mg/m ² /day) x5days	MX (mg/m ²)
Level -1	100	15
Level 1	150	15
Level 2	150	30
Level 3	150	60
Level 4	150	90
Level 5	150	120
Level 6	150	150

Level 7	200	150
---------	-----	-----

Cohort B (eligible patients with CNS disease)

Dose Level	DOSE-ESCALATION SCHEDULE	
	Dose	
	TMZ (mg/m ² /day) x5days	MX (mg/m ²)
Level -1	75	15
Level 1	100	15
Level 2	150	15
Level 3	150	30
Level 4	150	60
Level 5	150	120
Level 6	150	150
Level 7	200	150

For each cohort, 3 patients will be entered sequentially to each dose level.

- If none of the 3 patients at a dose level experience dose limiting toxicity (DLT) during the first cycle, new patients may be entered at the next higher dose level.
- If 1/3 patients experience a DLT during the first cycle, up to 3 more patients will be treated at the same dose level. If the 1st patient in the expanded cohort (4th at the given DL), experiences no DLT, then the remaining 2 patients can start treatment without a necessary delay.
 - As of protocol v22, if 1/3 patients experience any DLT that is not of a CNS nature in Cohort B dose level 6, we will continue dose escalation to dose level 7 since we have already treated three subjects in Cohort A dose level 6 and seven subjects in Cohort A dose level 7, none of whom experienced non-CNS toxicities
- If 2 or more experience DLT during the first cycle, no further patients are started at that dose and the MTD is the highest dose level in which <2 (of 6) patients develop DLT.
- If the final dose level is deemed the MTD, 6 patients will be treated at this dose level even if a DLT has not been observed.

Select non-hematologic grade 3 or 4 or hematologic grade 4 drug-related toxicities (CTC version 3.0) occurring within the first 28 days of the study will be considered a DLT.

Cohort A, Dose level 1: Two DLTs were observed in Dose Level 1 of Cohort A: grade 3 psychosis and grade 3 allergic reaction. Upon further review of the hypersensitivity reaction, it is believed that this was an idiosyncratic event, and further expansion of this

dose level is warranted. Dose level 1 of Cohort A will be expanded to 10 evaluable patients. Further dose escalation will occur only if less than 4 out of the 10 patients experience a DLT. Enrollment to subsequent dose levels will follow the rules outlined above.

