4.2 Definition of Dose-Limiting Toxicity (DLT) and Criteria for Dose Escalation

DLT in a given patient is defined as any grade III non-hematologic (thought to be MX related) or IV non-hematological toxicity or any grade IV anemia, neutropenia or thrombocytopenia lasting greater than 7 days, that is felt to be related to MX or the MX + TMZ drug combination occurring during the first cycle of treatment.

MTD (maximum tolerated dose) will be defined based on the toxicities observed during the first cycle of treatment

Definition of MTD: The MTD is defined as the highest dose tested in which none or only one patient experienced DLT attributable to the study drug combination, when at least six patients were treated at that dose and are evaluable for toxicity. The MTD is one dose level below the highest dose tested in which 2 or more patients experienced DLT attributable to the study drug. At least 6 patients will be treated at the MTD.

Management and dose modifications associated with the above adverse events are outlined in Section 5.

Special consideration is given to the evaluation of neurologic toxicity given the animal toxicity data and CNS involvement of a proportion of eligible patients.

Specifically:

- all patients will be evaluated by a staff Neurologist prior to initiation of treatment
- patients will undergo frequent (every 4-8 hours) neurologic checks by a CRU RN during the 1-day inpatient CRU stay on the first day of treatment.
- Patients will be evaluated by the covering Oncology clinician during the 1-day inpatient CRU stay on cycle 1.

A neurology consult will be obtained for any observed treatment-related neurologic toxicity \geq grade 2. For patients enrolled in cohort B (patients with CNS disease) with pre-existing neurologic toxicity cleared for participation by the neuro-oncology team, a neuro-oncology or neurology consult will be obtained for any observed treatment-related worsening in neurologic toxicities.

Dose escalation will proceed within each cohort according to the following scheme. DLT is defined above.

Number of Patients with DLT at a Given Dose Level	Escalation Decision Rule
0 out of 3	Enter 3 patients at the next dose level.
≥ 2	Dose escalation will be stopped. This dose level will be declared the maximally administered dose (highest dose administered). Three (3) additional patients will be entered at the next lowest dose level if only 3 patients were treated previously at that dose.

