5. DOSING DELAYS/DOSE MODIFICATIONS

On the day of starting each cycle, neutrophil and platelet hematologic parameters must have returned to eligibility values. Furthermore, grade 3 non-hematologic toxicity that is felt to be drug related must return to a grade 2 or better. If these criteria are not met, therapy will be held by 1 week increments for a maximum of 2 weeks. If treatment cannot be given during that time frame the patient will be removed from study.

Any grade 4 hematologic toxicity will result in a dose reduction to the lower dose level for methoxyamine/temozolomide. If this occurs at dose level 1, the dose of temozolomide will be decreased to dose level -1 (75 mg/m²/d for 5 days if in the CNS cohort; 100mg/m² for 5 days if in the non-CNS cohort).

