6.1.7 Route of Administration – Oral

6.1.8 Toxicity - The incidence of adverse events in the 158 patients in the Anaplastic Astrocytoma study for whom data are available. In the absence of a control group, it is not clear in many cases whether these events should be attributed to temozolomide or the patients' underlying conditions, but nausea, vomiting, fatigue and hematologic effects appear to be clearly drug-related. The most frequently occurring side effects were nausea, vomiting, headache and fatigue. The adverse events were usually NCI Common Toxicity Criteria (CTC) Grade 1 or 2 (mild to moderate in severity) and were self-limiting, with nausea and vomiting readily controlled with antiemetics. The incidence of severe nausea and vomiting (CTC grade 3 or 4) was 10% and 6%, respectively. Myelosuppression (thrombocytopenia and neutropenia) was the dose-limiting adverse event. It usually occurred within the first few cycles of therapy and was not cumulative.

Myelosuppression occurred late in the treatment cycle and returned to normal, on average, within 14 days of nadir counts. The median nadirs occurred at 26 days for platelets [range 21-40 days] and 28 days for neutrophils [range 1-44 days]. Only 14% (22/158) of patients had a neutrophil nadir and 20% (32/158) of patients had a platelet nadir which may have delayed the start of the next cycle. (See **WARNINGS**). Less than 10% of patients required hospitalization, blood transfusion or discontinuation of therapy due to myelosuppression.

In clinical trial experience with 110-111 women and 169-174 men (depending on measurements), there were higher rates of Grade 4 neutropenia (ANC < 500 cells/ μ L) thrombocytopenia (< 20,000 cells/ μ L) in women than men in the first cycle of therapy: (12% versus 5% and 9% versus 3%, respectively).

In the entire Safety database for which hematologic data exist (N= 932), 7% (4/61) and 9.5% (6/63) of patients over age 70 experienced Grade 4 neutropenia or thrombocytopenia in the first cycle, respectively. For patients less than or equal to age 70, 7% (62/871) and 5.5% (48/879) experienced Grade 4 neutropenia or thrombocytopenia in the first cycle, respectively.

Data released by the European Organization for Research and Treatment of Cancer (EORTC) in January 2014 shows that amongst 44 patients receiving temozolomide

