8. STUDY CALENDAR

Baseline evaluations are to be conducted within 2 weeks prior to start of protocol therapy. Scans and x-rays must be done \leq 4 weeks prior to the start of therapy. In the event that the patient's condition is deteriorating, laboratory evaluations should be repeated within 48 hours prior to initiation of the next cycle of therapy.

	Pre-study	C1 Wk 1	C1 Wk 2	C1 Wk 3	C1 Wk 4	Cx Wk 1 ^f	Cx Wk 2	Cw Wk 3	Cx Wk 4	Off study
Physical exam	X	X				X				X
Neurologic exam	X ^d									
MMSE	X ⁱ									
Vital signs	X	X								X
Heights	X									
Weight	X	X								X
Performance Status	X	X								X
CBC w/diff, plts	X	X	X	X	X	X ^j			X ^j	X
Serum chemistry^a	X	X	X	X	X	X				X
Serum tumor specific tumor markers^g	X									X
EKG (as indicated)	X	X								
Adverse event evaluation			X	X	X	X	X			
Tumor measurements^h	X	Tumor measurements are repeated at week 8, then every 8 weeks. Documentation (radiologic) must be provided for patients removed from study for progressive disease.								X
B-HCG	X ^b									
Pharmacokinetics^e, Lab Correlates		X ^c								

- a: Albumin, alkaline phosphatase, total bilirubin, bicarbonate, BUN, calcium, chloride, creatinine, glucose, LDH, phosphorus, potassium, total protein, SGOT [AST], SGPT [ALT], sodium.
- b: Serum pregnancy test (women of childbearing potential).
- c: See section 7.0. Pharmacokinetics will be done during week 1.
- d: All patients will be evaluated by a staff Neurologist prior to initiation of treatment and then will undergo frequent (every 4-8 hours) neurologic checks by a CRU RN during the 1-day inpatient CRU stay on cycle 1, day1.
- e: Pharmacokinetics will be obtained for the first cycle only.
- f: Subsequent cycles and associated evaluations may be conducted within +/- 2 days of the previous cycle.
- g: Tumor specific tumor markers to be obtained per physician discretion (CEA, CA 19-9, CA 125, etc) if appropriate.
- h: For cohort A, CT of the chest, abdomen and pelvis will be obtained. For cohort B, CT of the chest, abdomen and pelvis as well as MRI of the brain will be obtained if malignancy is a non-CNS primary. For primary brain tumors, CT of the chest, abdomen and pelvis not required.
- i: MMSE to be done at screening for subjects in Cohort B only. These subjects must have a score of < 15. See appendix D.
- j: CBCs to be done Days 1 and 22 for Cycles 2 and beyond, for both Cohorts.

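### The 28-day hematologic DLT window closes at the median neutrophil nadir and two days after the median platelet nadir given in Section 6.1.8, so late cycle 1 cytopenia does not count toward escalation

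*Combined protocol and SAP*

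**What the plan says.** **The window.** Section 4.1, and the Schema in near-identical words, define DLT from select grade 3 or 4 non-hematologic and grade 4 hematologic events: "drug-related toxicities (CTC version 3.0) occurring within the first 28 days of the study will be considered a DLT". Section 4.2 names no day. It requires toxicity "felt to be related to MX or the MX + TMZ drug combination occurring during the first cycle of treatment". The Schema sets cycle length at 28 days.

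**The threshold.** Section 4.2 adds a duration that the Schema and 4.1 lack: "any grade IV anemia, neutropenia or thrombocytopenia lasting greater than 7 days".

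**When marrow toxicity appears.** Section 6.1.8 calls myelosuppression the dose-limiting adverse event of temozolomide and reports: "The median nadirs occurred at 26 days for platelets [range 21-40 days] and 28 days for neutrophils [range 1-44 days". It adds: "Myelosuppression occurred late in the treatment cycle and returned to normal, on average, within 14 days of nadir counts".

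**When counts are taken.** The Section 8 calendar has a CBC in each of weeks 1 to 4 of cycle 1, with no day fixed. Footnote j applies to later cycles: "CBCs to be done Days 1 and 22 for Cycles 2 and beyond, for both Cohorts". Section 5 requires neutrophils and platelets to be back at eligibility values on the day a cycle starts. Otherwise, "therapy will be held by 1 week increments for a maximum of 2 weeks".

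**The concern.** The protocol expects low counts at the start of cycle 2, since Section 5 checks for them and holds treatment. In the study that Section 6.1.8 describes, nadirs that may have delayed the next cycle were not rare: "Only 14% (22/158) of patients had a neutrophil nadir and 20% (32/158) of patients had a platelet nadir which may have delayed". Yet no section says that such a finding enters the escalation decision.

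The primary objective is the MTD, decided on 3 to 6 patients per level, so one uncounted DLT can turn expansion into escalation, or stopping into escalation. The toxicity at issue is also one that MX may worsen. Section 6.2.3 reports that temozolomide neutropenia in rats increased with MX dose, although the effect on marrow colony assays, human cells included, was only mild.

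The v22 rule for Cohort B level 6 relies on the absence of non-CNS toxicities at Cohort A levels 6 and 7. If that statement refers to DLTs, it rests on the same window.

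**Working it through.** **1. Window against nadir.** Days are taken as counted from day 1 of the cycle (assumption).

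| | Median nadir | Window end minus median | Latest nadir | Latest minus window end |
|---|---|---|---|---|
| Platelets | day 26 | 28 − 26 = 2 days | day 40 | 12 days |
| Neutrophils | day 28 | 28 − 28 = 0 days | day 44 | 16 days |

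By the definition of a median, at most half of platelet nadirs fall after day 28, and probably fewer. For neutrophils it is about half, less any that fall on day 28 itself.

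**2. Counts near the boundary.** Planned cycle 2 day 1 is day 29, just outside the window. Footnote f allows ±2 days, so the clearance count could fall anywhere from day 27 to day 31. Whether the same low count lies inside the window could then depend on scheduling. If the week 4 CBC is drawn on day 22 (an assumption borrowed from footnote j), no count is scheduled between day 22 and the clearance count.

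**3. Effect of the duration clause.** To last more than 7 days within a literal 28 days, an episode must begin by about day 28 − 7 = 21. That is the earliest platelet nadir reported. If onset by day 28 is enough, the loss is smaller. The text does not say which applies.

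**4. The plan's own table.** With true DLT rate p and q = 1 − p, P(escalate) = q³ + 3pq² × q³. At p = 0.2: 0.512 + 3(0.2)(0.64)(0.512) = 0.709.

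| p | 0.1 | 0.2 | 0.3 | 0.4 | 0.5 |
|---|---|---|---|---|---|
| Section 12 | 0.91 | 0.71 | 0.49 | 0.32 | 0.17 |
| Recomputed | 0.906 | 0.709 | 0.494 | 0.309 | 0.172 |

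The table is reproduced apart from a 0.01 difference at p = 0.4. It takes every DLT as observed.

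**5. Scenario from Section 6.1.8.** Pooling the two age groups, first-cycle grade 4 neutropenia is (62 + 4)/(871 + 61) = 66/932 = 7.1%, and thrombocytopenia is (48 + 6)/(879 + 63) = 54/942 = 5.7%. The rate u of either lies between 7.1% (one nested in the other) and 12.8% (no overlap).

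Let g be the non-hematologic DLT rate, independent of u, and m the share of hematologic events missed. The true rate is 1 − (1 − g)(1 − u). The counted rate is 1 − (1 − g)(1 − u(1 − m)). Assume g = 0.10 and m = 0.5.

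| u | True rate | Counted rate | P(escalate), all counted | P(escalate), half missed |
|---|---|---|---|---|
| 7.1% | 0.164 | 0.132 | 0.786 | 0.849 |
| 12.8% | 0.215 | 0.158 | 0.675 | 0.798 |

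The gain is about 6 to 12 points. With g from 0.05 to 0.30 it is about 5 to 12 points. With the sex-specific rates in Section 6.1.8 and g = 0.10, it is about 4 to 7 points for men (5% and 3%) and 11 to 20 points for women (12% and 9%).

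**6. Bounds by hematologic share.** If a share h of DLTs is hematologic and m of those are missed, the counted rate is p(1 − hm). At p = 0.2 with m = 0.5, P(escalate) is 0.762 for h = 0.25, 0.814 for h = 0.5 and 0.906 for h = 1, against 0.709 with none missed. With h = 1 and m = 0.25 it is 0.814.

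**The case against.** **Section 4.2 says first cycle, not 28 days.** It is the section that defines DLT, and Section 5 can delay cycle 2 by up to two weeks. One could read a held cycle 1 as still open, so that late events are both seen and counted. This stands in part: the text does not prove that such events are excluded under 4.2. But the Schema ends cycles at 28 days, which makes the same window the natural reading, and 4.1 and the Schema give the day number outright.

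**A nadir is not a DLT.** This stands. Only grade 4 counts, for more than 7 days under 4.2, and it must be related to MX or the combination. Grade 4 can be reached before the nadir. A reader might infer that half of cycle 1 nadirs, and so half of hematologic DLTs, are never counted. The documents do not support that. The platelet median lies inside the window, half is at most a neutrophil figure, and the share of nadirs after day 28 is not the share of grade 4 onsets after day 28.

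**The data are borrowed.** The nadir figures are from temozolomide in an anaplastic astrocytoma study and are not stated to be cycle 1 data. The two DLTs that the protocol reports at Cohort A level 1, psychosis and allergic reaction, were both non-hematologic. Both points limit the size of the effect, not its direction.

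**The day 22 count is not stated for cycle 1.** This stands. A week 4 CBC could be drawn on any of days 22 to 28, so the conclusion does not rest on day 22.

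**Conclusion.** The concern holds in a limited form. Under the 28-day wording, hematologic observation stops at the median neutrophil nadir and two days after the median platelet nadir, with the reported ranges running 16 and 12 days further. Under 4.2 the status of a later event is at best undefined. To the extent that late grade 4 events occur and are left out, the hematologic DLT rate is too low and escalation is more likely than Section 12 shows.

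The size cannot be settled from the documents. The 6 to 12 points rest on temozolomide-alone grade 4 rates of any duration, a 10% non-hematologic rate and half of hematologic events missed. The last two are assumptions. A reader might infer the larger shift, from 0.71 to 0.91 at a true 20% rate (or 0.49 to 0.81 at 30%). That needs every DLT to be hematologic and half of them missed, and is an upper scenario only. This is an inexpensive improvement to the escalation endpoint, not evidence that the MTD is wrong.

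**What to change.** - Reconcile the 28-day, first-cycle and more-than-7-days wordings across the Schema, 4.1 and 4.2. State how an episode that starts before day 28 and continues past it is classified. Which grade and duration threshold applies is for the sponsor to settle.
- Run the hematologic DLT observation window through the count that clears cycle 2 day 1. When Section 5 holds cycle 2, extend the window through the hold (at most 2 more weeks).
- Score no patient as free of hematologic DLT until that count is available.

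**Cost.** The change is protocol wording, and Section 5 already requires the start-of-cycle counts. Escalation waits about a day for patients who recover on time and up to two weeks for a patient who has not. If the duration clause is kept, a grade 4 count first seen on day 29 can be classified only after day 29 + 7 = 36, which is within a hold ending about day 29 + 14 = 43.

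**Limit.** A patient who clears cycle 2 and reaches a nadir afterward would still be missed.
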